6.2 MACE

Propensity matched analysis: We will use the same matched sample described in section 6.1 to estimate the intervention effect on MACE using a Cox proportional hazards model stratified by matched pair.

Random Intercepts for Hospital: We will fit a Cox proportional hazards model with adjustment for the same selected patient characteristics and same propensity score as in the primary analysis. The only modification is that we will account for within hospital clustering using random intercepts for hospitals instead of robust standard errors.

7. References

2. Eldridge, S.M., D. Ashby, and S. Kerry, *Sample size for cluster randomized trials: effect of coefficient of variation of cluster size and analysis method*. Int J Epidemiol, 2006. **35**(5): p. 1292-300.
4. Ho, P.M., et al., *Multifaceted intervention to improve medication adherence and secondary prevention measures after acute coronary syndrome hospital discharge: a randomized clinical trial*. JAMA Intern Med, 2014. **174**(2): p. 186-93.
6. Austin, P.C., *Balance diagnostics for comparing the distribution of baseline covariates between treatments groups in propensity-score matched samples*. Statistics in Medicine, 2009. 28: p. 3083-3107.
7. Austin, P.C., *Some methods of propensity-score matching had superior performance to others: results of an empirical investigation and Monte Carlo simulations*. Biometrical Journal, 2009. 51: p. 171-184.

8. Appendices

8.2 Appendix: Table Shells

8.2.1 Main Table Shells

Table 1: Site Characteristics by Copayment Intervention

	Overall (N=)	Copayment Intervention (N=)	Usual Care (N=)
N patients enrolled			
MI volume			
% high (≥ 400) MI volume			
Site % baseline ticagrelor use			
% high ($\geq 15\%$) baseline ticagrelor use			
Region			
Randomization scheme			
Total bed size			
Teaching status			
Government hospital			
Member of a healthcare network			
Surgery capabilities			

Statistical Analysis Plan

Table 2a: Patient Level Baseline Characteristics by Copayment Intervention

	Overall (N=patients)	Copayment Intervention (N=patients)	Usual Care (N=patients)
Age			
Gender, % male			
Non-white race			
Hispanic ethnicity			
Private insurance			
Prior MI			
Prior PCI			
Prior CABG			
Prior stroke/TIA			
Prior heart failure			
Dialysis			
PAD			
Hypertension			
Diabetes			
Current/recent smoker			
Weight			
Transfer in			
STEMI			
Home P2Y12 inhibitor			
Home aspirin			
Creatinine Clearance			
Nadir hemoglobin			
Multivessel disease			
Access Site			
PCI performed			
CABG performed			
Drug-eluting stent			
In-hospital or prior bleeding			
In-hospital MI			
In-hospital stroke			
Cardiogenic shock (Killip IV on presentation or in- hospital cardiogenic shock)			

Statistical Analysis Plan

Heart failure (Killip II/III on presentation or in-hospital heart failure)			
Cardiac Arrest			
Health Literacy			
Baseline angina frequency			
Cardiac Rehab			
Baseline PHQ2>3			
Baseline EQ5D VAS			
Married			
Employed			
Education (college graduate)			
Baseline financial hardship			
Missed >1 dose of medication in the last month			

Statistical Analysis Plan

Table 2b: Cluster Level Summary Data of Baseline Characteristics by Copayment Intervention

	Overall (N=sites)	Copayment Intervention (N=sites)	Usual Care (N=sites)
Randomization Scheme			
Site MI volume			
Site % Ticagrelor			
Age			
Gender, % male			
Non-white race			
Hispanic ethnicity			
Private insurance			
Prior MI			
Prior PCI			
Prior CABG			
Prior stroke/TIA			
Prior Heart Failure			
Dialysis			
PAD			
Hypertension			
Diabetes			
Current/recent smoker			
Weight			
Transfer in			
STEMI			
Home P2Y ₁₂ inhibitor			
Home aspirin			
Creatinine Clearance			
Nadir hemoglobin			
Multivessel disease			
Access Site			
PCI performed			
CABG performed			
Bare Metal Stent			
In-hospital or prior bleeding			
In-hospital MI			
In-hospital stroke			

Statistical Analysis Plan

Cardiogenic shock (Killip IV on presentation or in-hospital cardiogenic shock)			
Heart failure (Killip II/III on presentation or in-hospital heart failure)			
Cardiac Arrest			
Health Literacy			
Baseline angina frequency			
Cardiac Rehab			
Baseline PHQ2>3			
Baseline EQ5D VAS			
Married			
Employed			
Education (college graduate)			
Baseline financial hardship			
Missed >1 dose of medication in the last month			

Statistical Analysis Plan

Table 3a: Clinical Outcomes by Copayment Intervention

Outcome	Cumulative Incidence at 12 months (95% CI)			Unadjusted		Adjusted	
	Overall (N=)	Copayment Intervention (N=)	Usual Care (N=)	HR (95% CI)	P- value	HR (95% CI)	P- value
MACE							
All-cause death							
MI							
Stroke							
BARC 2+ bleed							
BARC 3+ bleed							
GUSTO Moderate/Severe Bleed							
Unplanned Revascularization							
MACE + unplanned revascularization							
Cardiovascular death							

Statistical Analysis Plan

Table 3b: Subgroup Analysis of MACE by Copayment Intervention

Subgroup	Cumulative Incidence at 12 months (95% CI)			Unadjusted		Adjusted	
	Overall (N=)	Copayment Intervention (N=)	Usual Care (N=)	HR (95% CI)	P-value	HR (95% CI)	P-value
Age							
≥65							
<65							
Sex							
Male							
Female							
Insurance type							
Private							
Non-private							
Race							
White							
Non-white							
MI type							
STEMI							
NSTEMI							
In-hospital PCI							
In-hospital PCI							
No in-hospital PCI							

Statistical Analysis Plan

Table 4a. Medication Non-Persistence by Copayment Intervention

Outcome	Persistence at 12 months			Unadjusted		Adjusted	
	Overall (N=)	Copayment Intervention (N=)	Usual Care (N=)	OR (95% CI)	P-value	OR (95% CI)	P-value
Non-persistence to any P2Y ₁₂ vs. persistence							
Non-persistence or mortality to any P2Y ₁₂ vs. persistence							
Non-persistence to initial P2Y ₁₂ vs. persistence							

Statistical Analysis Plan

Table 4b. Subgroup Analysis of Medication Non-Persistence to Any P2Y₁₂ by Copayment Intervention

Subgroup	Persistence at 12 months			Unadjusted		Adjusted	
	Overall (N=)	Copayment Intervention (N=)	Usual Care (N=)	OR (95% CI)	P-value	OR (95% CI)	P-value
Age							
≥65							
<65							
Sex							
Male							
Female							
Insurance type							
Private							
Non-private							
Race							
White							
Non-white							
MI type							
STEMI							
NSTEMI							
In-hospital PCI							
In-hospital PCI							
No in-hospital PCI							

Statistical Analysis Plan

Table 5. ICCs

	Overall		Copayment Intervention		Usual Care	
	Unadjusted ICC	Adjusted ICC	Unadjusted ICC	Adjusted ICC	Unadjusted ICC	Adjusted ICC
MACE at 1 year						
Non-persistence to any P2Y ₁₂ vs. persistence						
Medication Selection at discharge						

Statistical Analysis Plan

Table 6. Medication Use by Patient Reported Persistence and Copayment Intervention in Substudies

Persistence Measure	Overall (N=X patients)		Copayment Intervention (N=X patients)		Usual Care (N=X patients)	
	Persistent	Not Persistent	Persistent	Not Persistent	Persistent	Not Persistent
P2Y ₁₂ Fill Persistence by 1 year						
P2Y ₁₂ Fill Adherence by 1 year						
Drug levels at 1 year						
Drug levels at 3 months						
Drug levels at 6 months						
Drug levels at 9 months						

Statistical Analysis Plan

Table 7. Kappa Statistics for Assessing Agreement with Patient reported persistence to any P2Y₁₂ at 1 year

Persistence Measure	Overall (N=X patients)		Copayment Intervention (N=X patients)		Usual Care (N=X patients)	
	Kappa (95% CI)	P- value*	Kappa (95% CI)	P-value*	Kappa (95% CI)	P- value*
P2Y ₁₂ Fill Persistence by 1 year						
P2Y ₁₂ Fill Adherence by 1 year						
Drug levels at 1 year						
Drug levels at 3 months						
Drug levels at 6 months						
Drug levels at 9 months						

*P-values are for test of Kappa = 0 (no more agreement than expected by chance).

Statistical Analysis Plan

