3.1 Non-persistence with antiplatelet therapy at 1 year

The co-primary endpoint of long-term non-persistence will be assessed using patient-reported medication non-persistence. Permanent and temporary discontinuation of a P2Y₁₂ receptor inhibitor will be queried at each follow-up interview. For patients with missing patient-reported medication information, pharmacy fill data will be used to ascertain persistence. Patients who have continued P2Y₁₂ receptor inhibitor use at one year from discharge with less than 30

Statistical Analysis Plan

continuous days of interruption will be considered persistent. We will use the last observation carried forward (LOCF) method for patients who died before one year or had missing 1 year P2Y₁₂ status.

The co-primary objective determines whether patient copayment reduction leads to higher long-term persistence with antiplatelet therapy at one year. The study endpoint for this objective is the proportion of patients at one year who had an interruption ≥ 30 days of P2Y₁₂ receptor inhibitor. The primary analysis will be a logistic regression model with parameters estimated using generalized estimating equations (GEE) to account for within hospital clustering and adjustment for selected patient characteristics (Section 8.3.1) which includes a propensity score for intervention (Section 8.3.2). The propensity score will be estimated using a logistic regression model for intervention group. Categorical variables will be included as sets of indicator variables. Continuous variables will be included assuming a simple linear relationship. Balance of covariates between intervention and usual care arms will be assessed using standardized differences as recommended by Austin [6]. We will assess functional form and possible transformations of the propensity score to be included in the outcome model. Cluster heterogeneity will be quantified using ICCs calculated from unadjusted and adjusted models. We will calculate the ICCs across all hospitals and also by treatment group.

After Steering Committee consensus, the randomization scheme was changed from 1:1 to 2:1 Usual Care vs. Intervention effective November 16, 2015. Randomization schema was added as a covariate for adjustment as shown in Section 8.3.1 and to the propensity model as shown in Section 8.3.2.

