4.4 Medication Drug Levels

Inclusion Criteria: All patients with valid drug level data.

A subset of patients will have blood drawn over the one year of follow-up after AMI. This blood draw will be randomly assigned to 250 patients (125 in each arm) at each of the following follow-up time points: 3, 6, 9, or 12 months. Drug levels or metabolites of clopidogrel or ticagrelor will be measured, as appropriate. Persistence (yes vs. no) will be defined based on clinically selected cut-offs of minimum drug levels. Medication drug level data will be presented in Table 6 in Section 8.2.1.

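### Table 7 sets drug levels drawn at 3, 6 and 9 months against self-reported persistence at one year, so truthful later stopping is scored as disagreement

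*SAP*

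**What the plan says.** Table 7 in SAP Section 8.2.1 names a single reference for all its rows: "Kappa Statistics for Assessing Agreement with Patient reported persistence to any" P2Y12 inhibitor at 1 year. The rows are fill persistence, fill adherence, drug levels at 1 year, and then "Drug levels at 3 months", "Drug levels at 6 months" and "Drug levels at 9 months". The footnote tests each kappa against zero.

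Table 6, "Medication Use by Patient Reported Persistence and Copayment Intervention in Substudies", has the same six rows and one Persistent / Not Persistent split in each column group. Its title does not say when persistence is assessed.

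Three sections of text bear on these shells:

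- **Section 4.4** assigns draws to 250 patients, 125 per arm, "at each of the following follow-up time points: 3, 6, 9, or 12 months". Drug-level persistence is yes or no by a cut-off on that sample.
- **Section 3.1** defines self-reported persistence over the whole year: still on treatment at one year, with no interruption of 30 days or more. It also says that discontinuation of a P2Y12 "receptor inhibitor will be queried at each follow-up interview".
- **Section 4.5** calls for kappa among patient-reported use, fills and drug levels. It gives no rule for matching times and refers to Table 7.

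**The concern.** A drug level shows whether the patient was taking the drug around the time of the draw. The Table 7 reference describes the full twelve months. A patient who has drug in the blood at month 3, stops at month 8 and reports this correctly lands in the cell for a positive level and non-persistence. Neither measurement is wrong, but kappa treats the pair as an error.

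The co-primary persistence endpoint rests on patient report in a trial whose SAP acknowledges the lack of blinding (Section 2). Among the measures in Table 7, drug levels are the only biological check on that report. A low kappa in the early rows could be taken as evidence against a sound endpoint. Conversely, real misreporting could be dismissed as a timing effect. The kappa summary alone cannot separate the two, and three of the four drug-level rows are affected.

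**Working it through.** **Inputs.** One-year persistence of 70% in the control arm (SAP Section 1.4). Draw times of 3, 6, 9 and 12 months, read as 250 patients at each (Section 4.4). The SAP states no expected kappa, so there is no planned figure to reproduce. As a check on the 70% input, the continuity-corrected chi-square calculation for 70% versus 74% returns 5392 patients at 90% power and 4622 at 85%, as Section 1.4 states.

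**Assumptions not in the SAP.** Self-report and assay are both error-free, and stopping is permanent. The timing of stopping within the year is unknown, so four patterns are used.

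**Formula.** Let s be the share on drug at the draw and p = 0.70 the share persistent at 12 months. The four cells are:

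- level positive, persistent: p
- level positive, not persistent: s − p
- level negative, persistent: 0
- level negative, not persistent: 1 − s

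Hence observed agreement is po = 1 − (s − p), chance agreement is pe = s·p + (1 − s)(1 − p), and kappa = (po − pe)/(1 − pe).

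**Worked case: 3 months, linear stopping.** s = 1 − 0.30 × 3/12 = 0.925. po = 1 − 0.225 = 0.775. pe = 0.925 × 0.70 + 0.075 × 0.30 = 0.670. Kappa = 0.105/0.330 = 0.318.

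**All patterns at p = 0.70.**

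| Timing of stopping | s at 3, 6, 9 months | kappa at 3, 6, 9 months |
|---|---|---|
| Linear | 0.925, 0.850, 0.775 | 0.32, 0.58, 0.81 |
| Constant hazard, s = 0.70^(t/12) | 0.915, 0.837, 0.765 | 0.36, 0.63, 0.83 |
| Half of stops by month 3 | 0.850, 0.800, 0.750 | 0.58, 0.74, 0.88 |
| Half of stops after month 9 | 0.950, 0.900, 0.850 | 0.22, 0.41, 0.58 |

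At 12 months s = p, so kappa is 1.00 in every pattern. With a same-time reference the discordant cell is empty at every draw, and the same data give 1.00 throughout.

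**False discordance per 250 patients, linear stopping.** 250 × (s − 0.70) gives about 56, 38 and 19 at 3, 6 and 9 months.

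**Sensitivity to persistence.** At 85% persistence with linear stopping, kappa is 0.36, 0.63 and 0.84. Over all four patterns and persistence from 70% to 85%, the 3-month value runs from 0.22 to 0.63.

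**Between arms.** With 70% versus 74% and linear stopping in both arms, kappa is 0.318 versus 0.330 at 3 months, 0.583 versus 0.597 at 6, and 0.808 versus 0.816 at 9. The gaps are about 0.01. The simple standard error √(po(1 − po)/n)/(1 − pe) with n = 125 and p = 0.70 is about 0.11, 0.09 and 0.06, before any allowance for clustering.

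**The case against.** The best defence is that the most important information survives. In an unblinded trial the main worry is over-reporting: the patient claims persistence but has no drug in the blood. Because persistence excludes any gap of 30 days or more, a negative level at month 3, 6 or 9 in a patient reported as persistent remains informative. Later stopping fills only the opposite cell. Table 6 shows the two columns separately, and Table 8 gives durations of use. This stands, and it confines the damage to the kappa summary. It does not rescue that summary, which merges both kinds of discordance.

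Several stronger readings are tempting but not supported:

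- **Table 6 makes the same explicit error.** Its title gives no time point. The one-year reading is inferred from its single split and its pairing with Table 7. The text of Section 4.5, which speaks of patient-reported medication use, would permit a same-time comparison.
- **All of Table 7 is affected.** The 1-year drug-level row and the two pharmacy-fill rows do not have this timing problem. The 1-year row can still disagree for patients who restart after a long gap: if 20% of non-persistent patients are back on drug at 12 months, kappa is about 0.85. That is a separate matter.
- **Kappa will differ by arm for this reason.** Under the planned 70% versus 74% the gap is about 0.01, well inside sampling error. Only a difference in the timing of stopping could make it matter, and the SAP gives no sign of one.
- **The co-primary result is at risk.** Tables 6 and 7 are descriptive. No threshold, decision rule, primary test or sample size depends on them, and Section 1.4 plans validation of self-report with pharmacy records.

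It is also fair to say that 1.0 is an ideal that requires error-free measurement, and that last observation carried forward for deaths and missing one-year status (Section 3.1) would remove some of the discordance.

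**Conclusion.** The concern holds for the 3-, 6- and 9-month drug-level rows of Table 7, where the mismatch is stated outright, and probably for the same rows of Table 6. No other section repairs it. With perfect reporting and a perfect assay, kappa at 70% persistence would be about 0.22–0.58, 0.41–0.74 and 0.58–0.88 at the three draws. These values depend on the assumed timing of stopping, on permanent stopping and on the 70% figure. The direction does not depend on the pattern: any real stopping between the draw and month 12 adds false discordance. The consequence is a misleading validation statistic. The primary analyses are not affected. The correction should be made because it is cheap and the statistic bears on the credibility of a self-reported co-primary endpoint.

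**What to change.** In Section 4.5 and in the 3-, 6- and 9-month drug-level rows of Tables 6 and 7, compare each drug level with patient-reported current P2Y12 use at the interview nearest the draw, overall and by arm. Report each time point separately. Keep one-year patient-reported persistence as the reference for the 1-year drug-level row and for the pharmacy-fill rows; the 1-year row is the contemporaneous biological check on the endpoint itself and should not be lost. Retitle Table 7 so that it no longer names one reference for all rows, and state the reference time in Table 6.

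The cost is a change to two shells and a sentence of text. Section 3.1 has discontinuation asked at every follow-up interview, so the reports should be available. The SAP does not give the interview months, which is why the nearest interview is a safer rule than the same visit.

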Patient-reported persistence to antiplatelet therapy will be validated using pharmacy records that will be collected on a subset of the overall study population. The assumed standard deviation of 0.25 (for the proportion of days covered) is based on a recent randomized clinical trial to assess an intervention designed to improve adherence [4]. Assuming 1:1 randomization and a two-sided Type I error rate of 0.05, a sample size calculation based on the two-sample t-test suggests that a total sample size of 1644 patients will yield 90% and a total sample size of 2034 will yield 95% power. A random sample of 2400 patients from the 300 sites randomized with a CV of 0.25 and an ICC of 0.025 would yield a design effect of approximately 1.26. The resulting effective sample size of 2021 patients would yield approximately 95% power to detect a difference of 4% between the patient copayment reduction intervention and control groups. The target sample size of 2500 patients with pharmacy records allows for 4% missing data due to records that are not available.

2. General Considerations for Data Analysis

We will include a detailed flow diagram showing the number of participants' eligible, number of subjects randomized to Copayment Intervention and Usual Care arms, numbers of subjects lost to follow-up or excluded from analyses, and the number of subjects analyzed for the key study endpoints. Additionally, we will describe the number of clinical sites in Copayment Intervention and Usual Care arms including the mean (median, range) for key study elements by site. Key elements will include the following items: descriptions of participants, interventions, objectives, outcomes, and sample size justification; and details about the randomization procedure, factors used to stratify randomization, (lack of) blinding, statistical methods, participant flow, dates of recruitment, baseline data by individuals and by cluster, numbers analyzed, outcomes and estimation, adverse events, and a discussion. These elements are based on the CONSORT statement for cluster randomized studies [5].

After Steering Committee consensus, the randomization scheme was changed from 1:1 to 2:1 Usual Care vs. Intervention effective November 16, 2015. Randomization schema was added below as a covariate for adjustment.

All analyses will be conducted using SAS version 9.4 or higher software. All tests will be two-sided and a p-value of <0.05 will be considered statistically significant.

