4.5 Comparison of Medication Use from different sources

Overall and stratified by copayment reduction, we will assess agreement among patient reported medication use, medication fill adherence, and drug levels using Kappa statistics and summarize using frequencies and percentages (Table 7 in Section 8.2.1).

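### The only planned test of agreement for self-reported persistence is kappa = 0, which very weak agreement passes and which cannot show whether misreporting differs between arms

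*SAP*

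**What the plan says.** Under SAP Section 3.1 the persistence co-primary "will be assessed using patient-reported medication non-persistence". Section 2 lists lack of blinding among the items to report, and a patient who uses a copayment voucher knows it.

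Section 1.4 states the safeguard: "Patient-reported persistence to antiplatelet therapy will be validated using pharmacy records that will be collected on a subset of the overall study population". Section 4.5 gives the method: "Overall and stratified by copayment reduction, we will assess agreement among patient reported medication use, medication fill adherence, and drug levels using Kappa statistics", with frequencies and percentages as a summary.

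Table 7 carries this out with a kappa, a 95% CI and a p-value for each measure, overall and in each arm. Its footnote says "P-values are for test of Kappa = 0 (no more agreement than expected by chance". The general rule in Section 2 is "All tests will be two-sided and a p-value of <0.05 will be considered statistically significant".

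Three other planned items are relevant:
- Table 6 cross-tabulates fill persistence, fill adherence and drug levels against patient-reported persistence, by arm.
- Section 4.3 compares fill-based persistence and adherence between arms by GEE logistic regression.
- Section 4.4 adds drug levels in 250 patients (125 per arm) at each time point.

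The SAP sets no acceptable level of agreement and no between-arm contrast of reporting error.

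**The concern.** Two measures of the same behaviour will nearly always agree better than chance, so rejecting kappa = 0 is little evidence that self-report is good enough to carry a co-primary endpoint.

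The error that would bias the arm comparison is differential. If patients who have stopped claim persistence more often in the voucher arm, or if patients who continue are wrongly recorded as stopped more often in usual care, a benefit appears that is not there. The reverse pattern hides a real one. A kappa = 0 test within each group does not address this. Kappa also merges over- and under-reporting into one number, so even a comparison of the two arm kappas would not isolate the error. What is at stake is whether a 4-point gain in reported persistence can be read as a gain in persistence.

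**Working it through.** **Inputs from the SAP.** 2400 pharmacy records from 300 sites, CV 0.25, ICC 0.025, 1:1 allocation (Section 1.4); control persistence 70% and target difference 4 points (Section 1.4); two-sided 0.05. All misreporting rates below are assumptions.

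**1. The plan's effective sample size.** Mean cluster size is 2400/300 = 8. The design effect is 1 + ((0.25² + 1) × 8 − 1) × 0.025 = 1.1875, and 2400/1.1875 = 2021, as stated. The printed design effect of 1.26 does not follow from CV 0.25; it matches CV 0.65 and would give 2400/1.26 = 1905. I use 2021.

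**2. Smallest kappa that is significant.** With both margins at 70%, chance agreement is 0.58 and the null standard error of kappa is 1/√n.
- Overall: 1.96/√2400 = 0.040; with effective n 2021, 0.044.
- Per arm: 1.96/√1200 = 0.057; with effective n 1010, 0.062.
- Drug levels: 1.96/√250 = 0.124; per arm 1.96/√125 = 0.175.

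At the pharmacy cut-offs observed agreement is 60–61% against 58% by chance.

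**3. A weak-agreement example.** Let 70% be persistent, 95% of them say so, and 90% of those who stopped also claim persistence. Observed agreement is 0.70 × 0.95 + 0.30 × 0.10 = 0.695. Reported persistence is 0.665 + 0.270 = 0.935. Chance agreement is 0.935 × 0.70 + 0.065 × 0.30 = 0.674. Kappa = (0.695 − 0.674)/(1 − 0.674) = 0.064. With null standard errors of 0.0141 (n = 2400) and 0.0200 (n = 1200), z is 4.6 overall and 3.2 per arm (p = 0.0013).

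**4. Equal kappas with a false benefit.** True persistence is 70% in both arms.

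| | Usual care | Intervention |
|---|---|---|
| Persistent patients who say so | 90% | 93.5% |
| Stopped patients who claim persistence | 40% | 45.6% |
| Reported persistence | 0.630 + 0.120 = 75.0% | 0.6545 + 0.1368 = 79.1% |
| Observed agreement | 0.810 | 0.818 |
| Chance agreement | 0.600 | 0.617 |
| Kappa | 0.525 | 0.525 |

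The false gain is 0.70 × 0.035 + 0.30 × 0.056 = 0.041. Both kappa = 0 tests reject (z about 18 to 19 at 1200 per arm).

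**5. The Section 4.3 comparison of fill persistence.** For 70% vs 74% with 1010 effective patients per arm, SE = √((0.21 + 0.1924)/1010) = 0.0200, so 0.04/0.0200 is about 2.0 and power is about 52%. If fill persistence is 70% in both arms, the 95% CI half-width is 1.96 × √(2 × 0.21/1010) = 4.0 points.

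**6. Precision of the missing contrast.** About 0.30 × 2400 = 720 patients are fill-non-persistent, 360 per arm. With an assumed design effect of 1.10 and over-reporting of 40% vs 50%, SE = √(1.10 × (0.24 + 0.25)/360) = 0.0387, a half-width of 7.6 points. That 10-point difference alone creates a false gain of 0.30 × 0.10 = 3 points. A full 4-point false gain needs 0.04/0.30 = 13.3 points; with about 303 effective patients per arm, power to detect it is about 91% to above 99% for usual-care over-reporting from 0 to 60%.

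In the step 4 example the over-reporting difference is only 5.6 points, inside that half-width. The under-reporting difference is 10% vs 6.5%; with 840 fill-persistent patients per arm and the same design effect its half-width is 1.96 × √(1.10 × (0.09 + 0.0608)/840) = 2.8 points. Both shares are therefore needed.

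**The case against.** The strongest reply is that the validation is wider than the footnote. A reader might infer that kappa = 0 is all the plan does to check self-report. The SAP does not support that. Section 4.3 compares fill-based persistence and adherence between arms without using the interview answer, so a gain produced purely by over-reporting would tend to vanish there. Table 7 gives a kappa interval by arm: if only over-reporting differs (40% vs 50%, with 95% of persistent patients reporting it), the kappas are 0.60 (0.55 to 0.65) and 0.51 (0.45 to 0.56), and a careful reader would notice. Table 6 holds the counts from which both misreporting shares can be worked out.

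A reader might also infer that p < 0.05 on kappa is the criterion for calling the endpoint validated. No section says so, and the p-value's null appears only in a table footnote. Nor would near-worthless agreement give p < 0.0001 in each arm: in the kappa 0.064 example the per-arm p is about 0.001. Finally, fill records are themselves imperfect, which gives a symmetric measure some justification.

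All of this stands, and it limits the point without removing it. Section 4.3 has about 52% power for the target difference and does not estimate reporting error. Kappa intervals can coincide while misreporting differs. Table 6 is laid out by self-report group and carries no arm difference or interval, whereas the shares needed condition on the pharmacy record.

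**Conclusion.** The point holds in a limited form. Kappa = 0 is the only planned test of agreement. It is passed at a kappa of about 0.04 overall and 0.06 per arm, and it cannot show whether misreporting differs between arms. The surrounding analyses are informative, but none estimates that difference, and a false gain of about 4 points is compatible with identical kappas.

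This rests on the SAP's 2400 records, 70% persistence and 1:1 allocation, on assumed misreporting rates, and on treating fill status as the reference. The shift to 2:1 randomization would widen the between-arm intervals somewhat. The point does not show that the co-primary is biased or that the plan would declare validation on a p-value. It is a worthwhile, inexpensive improvement and leaves the primary estimate, error rate and sample size as they are.

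**What to change.** In Section 4.5 and Table 7, drop the kappa = 0 p-values and keep kappa with its 95% CI as descriptive. Add to Table 6 or Table 7, by arm:

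- the share of fill-non-persistent patients who self-report persistence;
- the share of fill-persistent patients who self-report non-persistence.

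Give each with its between-arm difference and a hospital-robust 95% CI. State that these are read beside the Section 4.3 fill-based effect and that fill records are an imperfect reference. Limit the calculation to patients with an actual interview report: Section 3.1 lets pharmacy fills stand in for missing self-report, and including those patients would inflate agreement.

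The cost is some SAP wording and one revised or additional table shell, using data already planned. The drawback is limited precision, about ±7.6 points for the over-reporting difference. Fixing the contrast now avoids choosing it after the co-primary result is known.
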